6.4.1.2. Safety

No analysis windows are required for TEAEs, ISRs, Snellen visual acuity, confrontational visual field, and ocular motility assessments. Nominal visits will be used for summarizing Snellen visual acuity, confrontational visual field, and ocular motility assessments. Pronunciation videos

and facial sensation assessments will be summarized using analysis visit windows in [Table 6-3](#) and [Table 6-6](#) for the treatment group during the TP and MP, respectively, and in [Table 6-4](#) and [Table 6-5](#) for the control group during the CP and TP, respectively. Additionally, Jaw Functional Limitation Scale will be summarized using the analysis visit windows in [Table 6-7](#) for the treatment group during the TP and MP and in [Table 6-8](#) for the control group during the TP.

Table 6-7 Jaw Functional Limitation Scale Visit Windows for Treatment Group during the Treated and Maintenance Periods

Scheduled Visit for Safety Measure	Target Day of the Visit	Analysis Visit Window with Touch-up
Screening ^a	N/A	Screening visit; No more than 30 days prior to randomization
Baseline	N/A	Randomization/Initial Treatment visit
Day 14 After Initial Treatment	Day 15 Post Randomization/Initial Treatment	Day 2 to Day 23 of Randomization/Initial Treatment Period
Touch-up Treatment ^b	Day of Touch-up Treatment	Day 24 of Randomization/Initial Treatment Period to Touch-up Treatment Date
Day 14 After Touch-up Treatment	Day 15 Post Touch-up Treatment	Day 2 to Day 23 of Touch-up Treatment Period
Last Treatment ^c	Day of Last Treatment	Day of Last Treatment (Initial or Touch-up)
Month 1	Day 31 Post Last Treatment	Day 24 to Day 61
Month 3	Day 91 Post Last Treatment	Day 62 to Day 136
Month 6	Day 181 Post Last Treatment	Day 137 to Day 226
Month 9	Day 271 Post Last Treatment	Day 227 to Day 316
Month 12	Day 361 Post Last Treatment	Day 317 to Maintenance Treatment Date ^d or Study Exit Date, whichever is earlier
Maintenance Treatment ^d	Day 1 Maintenance Treatment	Day of Maintenance Treatment
Day 14 Maintenance Treatment	Day 15 Post Maintenance Treatment	Day 2 to Day 23 Post Maintenance Treatment
Month 1 after Maintenance Treatment	Day 31 Post Maintenance Treatment	Day 24 to Day 61 Post Maintenance Treatment
Month 3 after Maintenance Treatment	Day 91 Post Maintenance Treatment	≥ Day 62 Post Maintenance Treatment

^a Participants may have screening and randomization on the same day. In such cases, only randomization visit is relevant.

^b Not all participants will receive touch-up treatment.

^c Initial treatment if touch-up is not performed, otherwise touch-up treatment.

^d Not all participants will receive maintenance treatment.

Table 6-8 Jaw Functional Limitation Scale Visit Windows for Control Group during the Treated Period

Scheduled Visit for Safety Measure	Target Day of the Visit	Analysis Visit Window with Touch-up
Optional Treatment	N/A	Initial Treatment visit
Day 14 After Initial Treatment	Day 15 Post Initial Treatment	Day 2 to Day 23 of Initial Treatment Period
Touch-up Treatment ^a	Day of Touch-up Treatment	Day 24 of Initial Treatment Period to Touch-up Treatment Date
Day 14 After Touch-up Treatment	Day 15 Post Touch-up Treatment	Day 2 to Day 23 of Touch-up Treatment Period
Last Treatment ^b	Day of Last Treatment	Day of Last Treatment (Initial or Touch-up)
Month 1	Day 31 Post Last Treatment	Day 24 to Day 61
Month 3	Day 91 Post Last Treatment	Day 62 to Day 136
Month 6	Day 181 Post Last Treatment	Day ≥ 137

^a Not all participants will receive touch-up treatment.

^b Initial treatment if touch-up is not performed, otherwise touch-up treatment.

6.4.2. Missing Date Imputation

Missing date will only be imputed for TEAEs. Dates may be imputed with year, month, and day values under certain scenarios described in [Table 6-9](#).

Table 6-9 Imputation Scenarios

Scenario	Complete			Imputable
	Year	Month	Day	
1	Yes	Yes	Yes	Complete
2	Yes	Yes	—	Yes
3	Yes	—	Yes	No ^a
4	Yes	—	—	Yes
5	—	Yes	Yes	No ^a
6	—	Yes	—	No ^a
7	—	—	Yes	No ^a
8	—	—	—	Yes

^a Not allowed per database design.

6.4.2.1. Missing/Incomplete AE Start Date

For Scenario 2 (ie, if day is missing but month and year are available), the imputed day will be the first day of the month or the initial treatment date (randomization date for control group) if they have the same month and year, whichever is later (because TEAE onset is not expected prior to administration of study treatment);

CONFIDENTIAL

JUVÉDERM VOLUX™ XC

Statistical Analysis Plan V25L-002

For Scenario 4 (ie, if day and month are missing but year is available), the imputed day and month will be 01 Jan or the initial treatment date (randomization date for control group) if they have the same year, whichever is later.

For Scenario 8 (ie, if day, month, and year are all missing), the imputed start date is the initial treatment date for treatment group and the randomization date for control group.

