5.6.3. Adverse Events

An AE will be considered a TEAE if the AE began or worsened (increased in severity or became serious) on or after the date (and time, if known) of the initial treatment for the treatment group and on or after the date of randomization for the control group. An AE will be considered a TESAE if it is a TEAE that additionally meets any SAE criterion.

A TEAE will be considered a treatment-related AE if the TEAE is deemed related to the procedure or the study device by the TI.

CONFIDENTIAL

JUVÉDERM VOLUX™ XC

Statistical Analysis Plan V25L-002

An AESI is defined as any vision-related TEAE. The incidence of AESI will be summarized separately for CP, TP, and RP in descending order of PT, if the total number of participants with AESI is at least 5.

Overall summary will be provided on a per-participant level for TEAEs, treatment-related TEAEs, TESAEs, deaths, and TEAEs leading to study intervention discontinuation. If more than one event is coded to the same PT for the same participant, the participant will be counted only once for that PT using the greatest severity for the summarizations by severity and most related occurrence for the summarizations by relationship to study intervention. If the severity of a TEAE is missing, the maximum severity will be assigned to the event for the summarization by severity. The value will be displayed as missing in the data listing. If the relationship to the study intervention is missing for a TEAE, the event will be considered related to the study intervention for the summarization. The value will be displayed as missing in the data listing.

TEAEs will be summarized by treatment group for CP using the Safety population. TEAEs will also be summarized for TP and RP using the VT and VRT populations, respectively.

The number and percentage of participants with TEAEs and the events in the following AE categories will be summarized for the above populations as described in [Table 5-10](#). For participants who received maintenance treatment, their AEs reported during the three months in the initial treatment period will be summarized and presented in parallel with AEs reported during the maintenance treatment period.

Summary tables will be provided for participants with TESAEs and participants with TEAEs leading to discontinuation if these occurred in 5 or more participants. Listings of all TEAEs, AESIs, TESAEs, TEAEs leading to discontinuation, and death will be presented.

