taken on or after the start date of study treatment for treatment group or on or after the randomization date for control group.

Actual and change from baseline values for overall (including all items) and the 3 subscales of mastication, mobility, and verbal and non-verbal communication from the Jaw Functional Limitation Scale will be summarized using descriptive statistics by treatment group for the VT and VMT populations. The overall score will be computed as the mean of the available items. Details on the algorithm can be found in Section 6.5.3. Baseline for the control group during TP is defined as the last non-missing value prior to receiving optional treatment.

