6.4. Data Handling Convention

6.4.1. Analysis Window

6.4.1.1. Effectiveness

All scheduled and unscheduled visits with complete dates will be assigned visit windows and used for analysis (Table 6-3, Table 6-4, Table 6-5, and Table 6-6). However, if a scheduled visit with incomplete date is available with no other visits with complete date during the visit window, then the visit with incomplete date may be used for analysis, and the nominal visit will be used as the visit window (eg, if the only assessment collected for Month 3 visit window is on a Month 3 eCRF with incomplete date, then those data will be used for the Month 3 assessments).

For the treatment group, the effectiveness day is calculated relative to the last treatment date (either the initial treatment if no touch-up is performed, or the touch-up treatment, or the maintenance treatment date). If the analysis date is on or after the last treatment date, then the effectiveness day = analysis date - the last treatment date + 1. If the analysis date is before the last treatment date, then the effectiveness day = analysis date - the last treatment date.

For the control group during the no-treatment control period, the effectiveness day is calculated relative to the randomization date. If the analysis date is on or after the randomization date, then

effectiveness day = analysis date - randomization date + 1. If the analysis date is before the randomization date, then effectiveness day = analysis date - randomization date.

For the control group after receiving optional treatment, the effectiveness day is calculated relative to the last treatment date (either the initial treatment, if no touch-up is performed, or the touch-up treatment). If the analysis is on or after the last treatment date, then effectiveness day = analysis date - last treatment date + 1.

If there are multiple visits occurring within a single visit window with relevant data, the visit closest to the target day will be used in the analysis of the corresponding visit windows. If 2 visits are equal distance to the target day and are the same type of visit, then the later visit will be used.

Analysis visit windows for effectiveness endpoints are defined as follows:

If analysis date \geq reference date, then

$$\text{Analysis day} = \text{analysis date} - \text{reference date} + 1$$

If analysis date $<$ reference date, then

$$\text{Analysis day} = \text{analysis date} - \text{reference date}$$

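### SAP 6.4.2.1 sets no lower bound at the optional VOLUX injection when it imputes control-group AE start dates, so post-injection AEs can be dated into the Control Period

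*SAP*

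**What the plan says.** SAP 6.4.2 imputes dates only for treatment-emergent AEs (TEAEs). Section 6.4.2.1 covers three imputable patterns:

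- **Scenario 2, day missing:** "the imputed day will be the first day of the month or the initial treatment date (randomization date for control group"; the later of the two is taken if month and year agree. The reason given is "because TEAE onset is not expected prior to administration of study treatment".
- **Scenario 4, only the year known:** "the imputed day and month will be 01 Jan or the initial treatment date (randomization date for control group"; again the later, if the year agrees.
- **Scenario 8, nothing known:** "the imputed start date is the initial treatment date for treatment group and the randomization date for control group".

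The control anchor is randomization in all three. The optional injection is not mentioned.

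Other parts of the SAP treat that injection as a new starting point. Table 4-1 puts controls who receive it in the VOLUX Treated population. Table 5-1 ends their Control Period (CP) and starts their Treated Period (TP) on that date. Section 6.4.1.1 states: "For the control group after receiving optional treatment, the effectiveness day is calculated relative to the last treatment date". Section 5.6.6 states, for the Jaw Functional Limitation Scale: "Baseline for the control group during TP is defined as the last non-missing value prior to receiving optional treatment".

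AE tables are split by period. Section 5.6.3 says "TEAEs will be summarized by treatment group for CP using the Safety population", with separate summaries for later periods. Control-group TEAEs count from randomization.

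**The concern.** In a treated control, the start date decides whether an AE is reported as untreated or as following VOLUX. Optional treatment comes about six months after randomization, so a rule that looks back to randomization, 01 Jan or the first of the month can date a post-injection event before the injection. The event then leaves the treated-control TP summary and appears in CP, the only randomized safety comparison. Its duration (end minus start plus one) is overstated. The time-to-onset summary planned in SAP Table 5-9 would be negative if measured from the injection, though the SAP does not define its origin.

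The direction also differs from SAP 5.6.3, where missing severity is set to the maximum and missing relationship to related. Those gaps are resolved against the device; this one can be resolved in its favour.

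A related gap exists at maintenance: a fully undated AE that follows maintenance is dated to the initial treatment.

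**Working it through.** **The plan's own figures.** SAP Section 3 gives at least 144 and 48 randomized, with 5% and 15% lost before treatment. Rounding down, 144 × 0.95 = 136 and 48 × 0.85 = 40, total 176, as stated. The chance of seeing at least one AE of 1.5% incidence is 1 − 0.985^176 = 0.930, consistent with the stated minimum of 92%.

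**Participants exposed.** 48 × 0.85 = 40.8 and 54 × 0.85 = 45.9, so about 41 to 46 treated controls. With the rounded figures they are 40/176 = 23% of those treated.

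**Gap between anchors.** With a Month 6 window of ±10 days and up to 14 further days to treatment (Protocol Tables 4 and 5), the optional injection falls 180 − 10 = 170 to 180 + 10 + 14 = 204 days after randomization. Randomization is therefore never in the injection month.

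**When the imputed start precedes the injection**, for a true onset k days after it:

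- Scenario 2: onset in the injection month, and injection not on the 1st.
- Scenario 4: onset in the injection year, and injection not on 01 Jan.
- Scenario 8: always, by rule.

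**Shares.** Assume injection equally likely on each of the 731 days of 2019-2020 and k uniform within a window.

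Scenario 2, k = 0-29. A month of L days has L − 1 − k qualifying injection dates (none if negative). Summed over k, this gives 465 for L = 31, 435 for L = 30, 406 for L = 29 and 378 for L = 28. Total: 14 × 465 + 8 × 435 + 406 + 378 = 10,774. Divided by 731 × 30 = 21,930, this is 49.1%.

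Scenario 4. A year of Y days has Y − 1 − k qualifying dates.

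- k = 0-29: (30 × 364 − 435) + (30 × 365 − 435) = 21,000; /21,930 = 95.8%.
- k = 30-179: (150 × 364 − 15,675) + (150 × 365 − 15,675) = 78,000; /109,650 = 71.1%.
- k = 180-360: 181 × 94 + 181 × 95 = 34,209; /132,311 = 25.9%.

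| Onset after injection | Day missing | Only year known | Nothing known |
|---|---|---|---|
| Days 0-29 | 49% | 96% | 100% |
| Days 30-179 | 0% | 71% | 100% |
| Days 180-360 | 0% | 26% | 100% |

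The 49% averages over a steep decline. For fixed k up to 26 in a 365-day year the share is (365 − 12(k + 1))/365: 97% at day 0, 74% at day 7, 51% at day 14. It reaches 0% by day 30.

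**Example.** Randomized 10 Jul 2019, injected 20 Jan 2020, onset 22 Jan 2020. The imputed start is 1 Jan 2020 (Scenarios 2 and 4) or 10 Jul 2019 (Scenario 8), all in CP. If the event ended on 29 Jan 2020 (an assumed date), its true duration is 8 days; the rule gives 29 or 204. With the injection as lower bound, the start is 20 Jan 2020 and the duration 10 days.

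**Effect of one misplaced participant.** The treated-control TP rate falls by at most 1/40.8 = 2.5 points (1/45.9 = 2.2). If the event is shown in the Control column of CP, that rate rises by at most 1/48 = 2.1 points (1/54 = 1.9). Either change is zero if the person has another qualifying AE in the same row.

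**The case against.** Several objections stand and limit the point.

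- **A rule does exist.** A reader might infer that treated controls have no start-date rule. They do: 6.4.2.1 covers the whole control group. What is missing is a lower bound at the optional injection.
- **Self-contradiction is arguable.** A reader might say the rule contradicts its own stated reason. But SAP Table 4-1 counts control as a study treatment and 5.6.3 starts control TEAEs at randomization, so the anchor fits the SAP's TEAE definition. The rule is wrong for treated controls, but the section does not plainly contradict itself.
- **Damage to the randomized comparison is conditional.** The CP table uses the Safety population as treated. Table 4-1 footnote a assigns the control label to controls who do not take optional treatment and is silent on those who do, while Table 5-1 labels the control CP as Control. On one reading the event never enters the Control column, and 48 to 54 is not its denominator. It is still in the wrong period.
- **Double counting is not shown.** Table 5-1 shares boundary dates between control CP and TP, and between TP and the Maintenance Period (MP). The phrase "on or after the date (and time, if known) of the initial treatment for the treatment group" settles only TEAE status in the treatment group. The text permits an injection-day AE to be counted twice but does not require it. In the treatment group TP contains CP by design, so appearing in both is no error.
- **Practical safeguards are real.** AEs are solicited at every visit and call (Protocol 6.2), early injection-site responses go into a dated daily diary, and all TEAEs are listed. A related event shown as untreated would be noticeable. Listings reveal a misplaced event but do not correct the table.

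Assignment of AEs to periods by imputed start date is itself inferred from Table 5-1. The table specifications are in a separate document.

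**Conclusion.** The point holds in limited form. Followed as written, SAP 6.4.2.1 can date a treated control's post-injection AE before the injection, although the SAP re-anchors the same people for effectiveness and jaw function. The shares of 49%, 96% and 100% are conditional on an incomplete date, on period assignment by start date, and on uniform injection and onset dates; the 100% is true by construction. No absolute effect can be given, because the documents do not state how many dates are incomplete; the number is probably small.

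The sure consequences, given period assignment by start date, are a wrong period and an overstated duration. Entry into the Control column is possible but not established. The tables are descriptive and the primary endpoint is unaffected. The shared boundary day alone calls only for clarification. It matters more once the rule is corrected, because imputed starts will then often fall on that day. The correction is worth making because it is cheap.

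**What to change.** 1. **Optional injection.** In 6.4.2.1, for controls who received optional VOLUX, impute the start no earlier than the optional initial treatment date when (i) the known start-date parts are compatible with that date or a later one, and (ii) neither an observed AE end date nor the visit or call at which the AE was first recorded shows onset before the injection. Imputed end dates must not be used: 6.4.2.2 sets a fully missing end date to study exit, which can never show earlier onset. Name the eCRF field for the recording contact; if there is none, use the observed end date and known start-date parts alone. Under the working's assumptions, no true post-injection AE is then dated before the injection.
2. **Maintenance.** Use the maintenance date as lower bound only when the AE was first recorded after that injection and the known date parts allow it. Otherwise keep the present rule. A blanket bound would move every fully undated AE of a maintained participant from TP to MP, including events of the initial treatment, and is not shown to be conservative.
3. **Tie rule, for AE attribution only.** Assign AEs starting on the optional or maintenance injection day to the later period unless a recorded time shows onset before injection. Leave effectiveness period dates unchanged, so same-day Month 6 and Month 12 assessments stay where they are.
4. **Label.** State in Table 4-1 footnote a which CP column holds a treated control.

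The cost is SAP wording and one derivation. Some control-period AEs with no usable information may be attributed to VOLUX under item 1. That is conservative for the device, and the number should be few if incomplete dates are few. If the database is already locked, document the change as a deviation in the clinical study report, as Protocol Section 8 provides.

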6.4.2.2. Missing/Incomplete AE End Date

[figure not shown]
For Scenario 2 (ie, if day is missing but month and year are available), then the imputed day will be the last day of the month or the study exit date if they have the same month and year, whichever is earlier.

For Scenario 4, (ie, if day and month are missing but year is available), the imputed day and month will be 31 Dec or the study exit date if they have the same year, whichever is earlier.

For Scenario 8 (ie, if day, month, and year are all missing), the imputed date will be the study exit date.

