### 8.3.3 Other Effectiveness Analyses

# 8.3.4 Safety Analyses

Subject assessment of procedural pain score and of jaw function using the 20-item Jaw Functional Limitation Scale questionnaire will be summarized descriptively. Assessments from the pronunciation recordings and facial sensation assessment will be summarized descriptively.

Snellen visual acuity, confrontational visual fields, and ocular motility assessments will be summarized descriptively.

ISRs will be summarized by maximum severity and ISR days for initial, touch-up, and maintenance treatments, separately. Summaries will include the incidence rate for each ISR.

Treatment-emergent AEs and treatment-related AEs (ie, device- or procedure-related) will be summarized by System Organ Class and Preferred Term, and severity. In addition, treatment-related AEs will also be tabulated by duration, severity, causality, action taken, and outcome. The summary will include incidence rate as well as total number of events.

AEs that occur after obtaining written IC but before treatment will be listed, but not summarized.

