# 11.3 Procedures for Reporting an AE or ADE

All AEs or ADEs occurring during the study period (after signing of the ICF) are to be recorded on the appropriate eCRF.

If a treatment-related AE is ongoing at the time of exit, the TI will attempt to follow the subject until the AE has been resolved or follow-up is no longer possible. The TI shall ask for the subject's permission to follow his/her status/condition outside the study.

The TI will report AESIs to Allergan within 24 hours of awareness of the event by completing an AE eCRF and notifying Allergan study management personnel and the Medical Safety Physician by fax or email. Allergan will notify FDA of any AESI within 10 working days of Allergan's awareness of the event.

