- ! For applicable effectiveness and safety endpoints, baseline is defined as the last non-missing value on or before the latter of randomization date or first treatment date in the control period, unless otherwise specified.
- ! Descriptive statistics for continuous variables include the sample size (N), number of non-missing observations (n), mean, standard deviation, median, 1st and 3rd quartiles, minimum, and maximum. For continuous data, a 2-sample t-test or Wilcoxon rank test will be used for between group comparisons as appropriate, unless stated otherwise. Specified that 95% CI for continuous variables will be based on the standard normal distribution in Section 5.1.
- ! Summary statistics for categorical variables include the sample size (N1), frequency count, and percentage. Ordinal categorical variables will be analyzed using the Cochran-Mantel-Haenszel test. Nominal variables will be analyzed using Pearson's chi-squared test or Fisher's exact test as appropriate. The 95% CI will be computed using the exact binomial method.
- ! The level of significance used for all statistical tests will be 0.05, 2-sided, unless stated otherwise.
- ! The change from baseline values will be computed as the value for the post baseline visit minus the baseline value, unless otherwise indicated.
- ! In the event if any data collected was after exit, it will not be included in tables but will only be presented in the listings.
- ! All statistical analysis will be performed using SAS version 9.3 or higher.
- ! MedDRA 22.1 or newer will be used to code AEs and medical history.
- ! WHO Drug Dictionary 201703 or newer will be used to code medications.

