AEs that occur after obtaining written informed consent but before treatment will be listed, but not summarized.

The duration of an AE is defined as the end date of AE minus the start date of AE, plus 1.

Table 5-9 TEAE Summaries

Endpoint	Description	Timing	Methodology
Overall summary	Overall summary only for the following categories: ! TEAEs ! Treatment-related TEAEs ! Treatment-related TEAEs at injection site ! Treatment-related TEAEs not at injection site ! TESAEs ! Treatment-related TESAEs ! Treatment-related TESAEs at injection site ! Treatment-related TESAEs not at injection site ! Discontinued due to TEAE ! Deaths	CP, TP, MP	Categorical descriptive statistics, event descriptive statistics
TEAEs	! Overall summary and by SOC and PT ! Overall summary and by SOC, PT, and maximum severity	CP, TP, MP	Categorical descriptive statistics, event descriptive statistics
Treatment-related TEAEs	! Overall summary and by SOC and PT ! Overall summary and by SOC, PT, and maximum severity ! Overall summary by maximum severity, time to onset, duration, action taken, and outcome	CP, TP, MP	Categorical descriptive statistics, event descriptive statistics
TESAEs	Overall summary and by SOC and PT	CP, TP, MP	Categorical descriptive statistics, event descriptive statistics
AEs leading to discontinuation	Overall summary and by SOC and PT	CP, TP, MP	Categorical descriptive statistics, event descriptive statistics

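### The SAP gives a TEAE still ongoing at study exit a completed duration ending at exit, because its end-date rule does not separate ongoing events from events that ended on an unknown date

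*SAP*

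**What the plan says.** Five provisions bear on this point.

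- **Imputation (SAP 6.4.2 and 6.4.2.2).** Section 6.4.2 sets the scope: "Missing date will only be imputed for TEAEs". For an end date with no component recorded, 6.4.2.2 states: "For Scenario 8 (ie, if day, month, and year are all missing), the imputed date will be the study exit date". Neither section mentions events that are ongoing.
- **Duration (SAP 5.6.3).** "The duration of an AE is defined as the end date of AE minus the start date of AE, plus 1". There is no censoring rule.
- **Tabulation.** SAP Table 5-9 has this entry for treatment-related TEAEs, for the control, treated and maintenance periods: "Overall summary by maximum severity, time to onset, duration, action taken, and outcome". Protocol 8.3.4 likewise has it that "treatment-related AEs will also be tabulated by duration, severity, causality, action taken, and outcome".
- **Data after exit (SAP 5.1).** For anything collected after a participant leaves, "it will not be included in tables but will only be presented in the listings".
- **Follow-up after exit (protocol 6.5 and 11.3).** If a treatment-related AE is ongoing at exit, "the TI will attempt to follow the subject until the AE has been resolved or follow-up is no longer possible".

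**The concern.** An event that has not resolved has no end date. Under the SAP it looks the same as an event that ended on a date nobody recorded, and both receive the exit date. For the unresolved event, the only thing known is that it lasted at least until exit. The duration formula nevertheless turns that minimum into an ordinary observed value, and the table reader cannot tell it from a true one.

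The events affected are those that start late or persist. Protocol 11.1.1 lists delayed effects such as lumps, nodules and swelling that can appear many months after treatment, so onset close to exit is foreseeable. The protocol also asks the treating investigator to keep following treatment-related events after exit. The SAP does not say that what this yields may be used in the duration or outcome tables, and the general rule in 5.1 points the other way.

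**Working it through.** The documents state no figure for AE duration or for the number of AEs ongoing at exit, so there is no planned figure to reproduce. The check applies the SAP's own formula.

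**Inputs**
- Duration = end day − start day + 1 (SAP 5.6.3).
- End day = exit day when the end date is wholly missing (SAP 6.4.2.2, Scenario 8).
- Exit day = 361, the Month 12 target day after last treatment (SAP Table 6-3), for a treatment-group participant without maintenance treatment. Onset days are on the same clock.
- Persistence after exit = 30, 90 or 180 days. This is an assumption, used only to show a range.

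**Case A: event unresolved at exit.** Tabulated duration = 361 − onset + 1. True duration = (361 + persistence) − onset + 1. The shortfall equals the days of persistence after exit.

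| Onset | Tabulated | True, +30 days | True, +90 days | True, +180 days | Understated by |
|---|---|---|---|---|---|
| Day 331 | 361 − 331 + 1 = 31 | 61 | 121 | 211 | 49%, 74%, 85% |
| Day 181 | 361 − 181 + 1 = 181 | 211 | 271 | 361 | 14%, 33%, 50% |
| Day 31 | 361 − 31 + 1 = 331 | 361 | 421 | 511 | 8%, 21%, 35% |

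The percentage is shortfall over true duration; for onset Day 331 and 90 days of persistence it is 90/121 = 74%. The later the onset, the larger the relative error.

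**Case B: event resolved before exit, end date unknown.** The same rule now errs upward.

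| Onset | True end | True duration | Tabulated |
|---|---|---|---|
| Day 10 | Day 20 | 20 − 10 + 1 = 11 | 361 − 10 + 1 = 352 |
| Day 31 | Day 60 | 60 − 31 + 1 = 30 | 361 − 31 + 1 = 331 |
| Day 181 | Day 240 | 240 − 181 + 1 = 60 | 361 − 181 + 1 = 181 |

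One rule thus covers two different situations, with errors in opposite directions.

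**Case C: resolution date obtained after exit.** The end date is then complete, so Scenario 8 does not apply. Whether the date enters the duration table depends on SAP 5.1, which sends post-exit data to listings only and does not mention AE end dates. Read literally, 5.1 leaves the date out of the table. The SAP does not say what the table shows in its place.

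**The case against.** The case for leaving the text alone has several parts.

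- **The event is not misreported as resolved.** A reader might infer that unresolved events are reported as having ended at exit. That is true only of the duration calculation. The imputation does not touch the outcome field, outcome is tabulated for the same events, and all TEAEs are listed. This stands, although the same table could then show an unresolved outcome beside a completed duration.
- **The bias is not always downward.** A reader might infer that the rule understates duration throughout. Case B shows otherwise, and with no counts the net direction is unknown. This stands.
- **A known later end date is not expressly discarded.** A reader might infer that a resolution date found after exit is replaced by the exit date. Section 5.1 implies that it is kept out of tables but does not address AE end dates, and 6.4.2.2 does not say that a known date is overwritten. This is an ambiguity to close, not a stated rule.
- **Part of the limit is design.** AE collection ends at the last visit (protocol 11.2), and later follow-up is only attempted. After maintenance treatment, follow-up lasts 3 months with a 10-day window, so observed durations cannot go much beyond 100 days under any rule. Controls who leave at Month 6 without optional treatment have had no injection, so they give no support to an argument from differing exit times. Both points stand.
- **The effect on the table is not visible.** Table specifications are in a separate document. If duration is banded, truncation matters only when it moves an event to another band. This stands.

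None of these supplies a rule for ongoing events. The SAP text as written still presents a lower bound as an observed duration.

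**Conclusion.** The concern holds in a limited form. Followed as written, SAP 6.4.2.2 and 5.6.3 give a treatment-related TEAE unresolved at exit, with no end date, a completed duration that is short by the number of days it continues after exit. In the illustration this is 8% to 85% of the true duration, assuming exit on Day 361 and 30 to 180 days of persistence. For events that resolved earlier on an unknown date, the same rule overstates duration. SAP 5.1 adds a gap, because it makes no exemption for resolution dates sought under protocol 6.5 and 11.3.

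The consequence is confined to a descriptive safety summary. AE incidence, severity, outcome, listings and the effectiveness endpoints are unaffected. The number of affected events is not given, so the effect on the table as a whole cannot be computed. The documents do not support a claim of general understatement, or a claim that unresolved events are recorded as resolved. The change is worth making because the rule gives a wrong value for a foreseeable kind of event and is cheap to correct.

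**What to change.** Three edits to the SAP:

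1. In 6.4.2.2, limit end-date imputation to TEAEs recorded as resolved with a missing or incomplete end date.
2. In Table 5-9 and its table specification, show TEAEs ongoing at exit in a separate duration category, such as 'ongoing at exit (at least x days)', where x is exit minus onset plus 1. A time-to-resolution analysis is not needed for a descriptive table.
3. In 5.1, state that end dates and outcomes obtained after exit for treatment-related AEs under protocol 11.3 are used in the duration and outcome tables, as an exception to the listings-only rule.

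The upward error for resolved events with an unknown end date remains. It makes durations look longer rather than shorter, and a footnote giving the number of imputed end dates would show its extent.

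The cost is a few sentences and one extra table category, with no data collection beyond what the protocol already asks for. The downside is that reported durations may look somewhat less favourable.
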